7.5. Ventilatory parameters

Ventilatory parameters will be measured as detailed in the Time and Events table (Section 7.1).

Measurements may include change from baseline of oxygen consumption (VO₂), carbon dioxide production (CO₂) and other parameters as data permit

Further details can be found in the SRM.

7.6. Pulse Oximetry

Oxygen saturation will be monitored continuously via pulse oximetry as detailed in the SRM. Measurements to be taken at the same time as the echocardiograms and recorded in the eCRF.

7.7. Pharmacokinetics

7.7.1. Blood Sample Collection

Blood samples for pharmacokinetic (PK) analysis of GSK2586881 will be collected at the time points indicated in the Time and Events Table (Section 7.1). The actual date and time of each blood sample collection will be recorded.

The timing of PK samples may be altered and/or PK samples may be obtained at additional time points to ensure thorough PK monitoring.

Details of PK blood sample collection (including volume to be collected), processing, storage and shipping procedures are provided in the SRM.

7.7.2. Sample Analysis

Plasma analysis will be performed under the control of PTS, In Vitro/In Vivo Translations (IVIVT) Department and Third Party Resourcing (TPR), GlaxoSmithKline. The details of the Bioanalytical Laboratory will be included in the Study Reference Manual (SRM). Concentrations of GSK2586881 will be determined in plasma samples using the currently approved bioanalytical methodology. Raw data will be archived at the Bioanalytical Site (to be detailed in the SRM).

7.8. Biomarker(s)/Pharmacodynamic Markers

Blood samples for biomarker/PD analysis will be collected at the time points indicated in, the Time and Events Table (Section 7.1). The actual date and time of each blood sample collection will be recorded. The timing of biomarker/PD samples may be altered and/or samples may be obtained at additional time points to ensure thorough monitoring.

Details of biomarker/PD blood sample collection (including volume to be collected), processing, storage and shipping procedures are provided in the SRM.

7.8.1. Renin-angiotensin system biomarkers

RAS peptides including but not limited to AngII, Ang(1-7) and Ang(1-5) may be analysed as data permit.

7.8.2. Other Biomarkers

Peptide hormones such as Kinins (e.g. des-Arg-bradykinin), apelin (e.g. Apelin 13, pyr1-Apelin, 13) and other systems (e.g. dynorphin A) may be analysed as data permit.

Atrial Natriotic peptide (ANP), Brain Natrietic Peptide (NT-proBNP), Troponin I, Surfactant Protein D, IL-6 and/or additional analytes to be determined may also be analysed as data permit.

7.9. Genetics

Information regarding genetic research is included in [Appendix 3](#).

Genetic sampling is optional. Subjects can refuse PGx sampling but will still be allowed to participate in the study.

7.9.1. Blood sample collection

Blood samples to investigate the association between the loss of function polymorphism rs1799752, representing the I/D polymorphism, in intron 16 of the Angiotensin Converting Enzyme (*ACE*) gene and Ang II (and possibly other RAS peptides) and hypoxic pulmonary vasoconstriction will be collected as specified in the Time and Events Table (Section 7.1).

Further information for blood sample collection, processing, storage and shipping procedures are provided in the SRM.

Information regarding genetic research is included in [Appendix 3](#).

7.10. Immunogenicity

7.10.1. Sample collection

Blood samples for immunogenicity analysis will be collected at the time points indicated in Section 7.1, Time and Events Table. Additional visits to obtain immunogenicity samples may be required in the unlikely event that subjects develop a clinically relevant immunoglobulin response to the drug as described in the SRM.

Details of immunogenicity blood sample collection (including volume to be collected), processing, storage and shipping procedures are provided in the SRM.

7.10.2. Sample analysis

Immunogenicity analysis will be performed under the management of Clinical Immunology, Biopharm R&D, GlaxoSmithKline. All pre-dose and post-dose samples will be first tested for Anti-ACE2 binding antibodies by screening and confirmation assay steps. The post-dose samples tested positive for anti-ACE2 binding antibodies will be further characterized for anti-ACE2 neutralizing antibodies. Both positive incidences for anti-ACE2 binding and neutralizing antibodies will be reported.

8. DATA MANAGEMENT

- For this study subject data will be entered into GSK defined CRFs, transmitted electronically to GSK or designee and combined with data provided from other sources in a validated data system.
- Management of clinical data will be performed in accordance with applicable GSK standards and data cleaning procedures to ensure the integrity of the data, e.g., removing errors and inconsistencies in the data.
- Adverse events and concomitant medications terms will be coded using MedDRA (Medical Dictionary for Regulatory Activities) and an internal validated medication dictionary, GSKDrug.
- CRFs (including queries and audit trails) will be retained by GSK, and copies will be sent to the investigator to maintain as the investigator copy. Subject initials and day/month of birth will not be collected or transmitted to GSK according to GSK policy.

9. STATISTICAL CONSIDERATIONS AND DATA ANALYSES

9.1. Hypotheses

The focus of this study is on the exploration the effect of GSK2586881 on a range of echocardiography, pulse oximetry, biomarker, safety and PK endpoints, when subjecting healthy volunteers to an exercise challenge under hypoxic conditions. No formal statistical hypotheses are being tested. A Bayesian statistical analysis framework with non-informative priors for model parameters (unless otherwise specified) will be used to obtain posterior distributions for effects of interest. These posterior distributions will be used to obtain a number of probability statements about the magnitude of treatment effects (e.g. Probability of **any** treatment related reduction in PASP, or Probability that the treatment related reduction in PASP ≥ 5 mmHg).

A rule of thumb for end of “study success” is if the probability of any treatment related reduction in PASP (T3-T0) exceeds 0.95 (success is also conditional on the probability of (absolute) treatment related reductions in oxygen saturation exceeding 5% being small).

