Secondly, in the alternative case that the simulated treatment difference was in favour of GSK2586881 over Placebo, a posterior probability of success (where success was defined as a 97.5% posterior probability of the treatment difference being in favour of GSK2586881 over Placebo) was evaluated for 30 **20** subjects. This was evaluated using a t-distribution, with the mean and standard deviation taken as the treatment difference and standard error (multiplied by a factor of the square root of 45 **10** to estimate the standard deviation) from step one, respectively. If this posterior probability was less than 0.2, then the study was stopped for futility as being unlikely to show any benefit of GSK2586881 over Placebo.

Thirdly, provided that the simulated study hadn't been stopped for futility in either of the first two steps, posterior probabilities of success were calculated for N ranging from 45 **10** to 29 **19** subjects. If any of these posterior probabilities of success were greater than or equal to 0.9, then the study was continued with a reduced sample size equal to the lowest N at which that threshold was reached. Otherwise, the conclusion from the simulated interim analysis would be to continue the study with unchanged sample size.

This whole process (simulating data for 45 **10** subjects, modelling the treatment difference, evaluating posterior probabilities of success and simulating the decision-making process) was replicated 10000 times for each scenario, with the decision ("futile", "no change to N" or "reduce N") recorded for each iteration. Each combination of the four treatment difference scenarios and the four correlation scenarios was evaluated for a total of 16 scenarios in all.

The estimated proportions of each decision being reached under each of the 16 scenarios are presented in Table 4.

Table 4 Operating characteristics of interim analysis at N=10 under four scenarios of treatment effect and four scenarios of within-subject correlation

		Frequency of decisions (%)		
Treatment effect Scenario	Within-subject correlation of PASP	Futile	Continue with 20 30 subjects	Continue with reduced sample size
Δ=0 mmHg (no treatment difference)				
	0.0	87 85%	13 15%	0 1%
	0.3	87 85%	13 15%	1%
	0.6	85%	15%	0 1%
	0.9	86 85%	14%	0 1%
Δ=2.5 mmHg (weak treatment effect, less than clinically meaningful difference)				
	0.0	44 31%	50 60%	9 6%
	0.3	36 24%	56 65%	11 9%
	0.6	21 10%	63 66%	25 16%
	0.9	1 0%	31 9%	91 68%

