9.2. Sample Size Considerations

The sample size of 30 patients is based on logistical considerations and is not based on formal sample size calculations. However, estimates of precision for the treatment difference in the primary endpoint are presented for context. (Note: precision in this context is defined as one half of the width of the 95% confidence interval.) A sample size re-estimation is planned after 15 subjects.

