9.3.2. Interim Analysis

An interim analysis is planned after 15 subjects have completed the following critical assessments:

- PASP at T0 and T3 for both study periods
- Oxygen saturation at T0 and T3 for both study periods
- Adverse events

The interim analysis will use the following study data:

- PASP at time T0 and T3 for both periods, for the first 15 subjects
- Oxygen saturation at T0 and T3 for both periods, for the first 15 subjects
- Adverse events for the first 15 subjects
- Angiotensin biomarker concentrations for the first 5 subjects (to allow time for the samples to be analysed by the external lab).

The interim analysis will use a data snapshot that has been cleaned to the best extent allowed by the timeframes (i.e. the interim data will not be fully cleaned or fully QC'd data and there will not be a locked database).

The aims of the interim analysis, and the endpoints to be used to address them, are as follows:

- Using the primary endpoint (treatment differences between GSK2586881 and Placebo in change from pre-dose PASP to hypoxic/exercised PASP [T3-T0]):
 - To decide whether to continue the study or stop based on futility, and
 - to conduct an advisory sample-size re-estimation with the view to potentially reduce the number of subjects participating in the study below 30.
- Using secondary endpoints:
 - to estimate treatment differences between GSK2586881 and Placebo in change from pre-dose oxygen saturation to hypoxic/exercised oxygen saturation [T3-T0], with a view to stopping the study if there is evidence that GSK2586881 causes a reduction in oxygen saturation in healthy volunteers. As a non-binding guide high posterior probability of observing $\geq 5\%$ absolute differences in **mean** oxygenation saturation values between placebo and active arms would be of concern; but clinical judgement would override any statistical methods if, for example, the majority of subjects displayed consistent patterns of reductions e.g. between 2-3%).

- to compare adverse events within the two treatment groups and explore any potential safety signals that may emerge

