To assess the operating characteristics of the interim analysis decisions to be made based on the primary endpoint, a simulation was carried out to estimate the relative proportion of studies reaching conclusions to stop for futility, continue with no change to the sample size, and to continue with a reduced sample size, under various different scenarios of the true treatment effect. Broadly speaking, the aim of the simulation was to confirm that (in an overwhelming majority of cases) a decision to stop for futility would be reached in the case of no true treatment effect and a decision to continue (perhaps with reduced sample size) would be reached in the case of a true treatment effect.

Simulated datasets of PASP at baseline (i.e. normoxic and at rest) and under hypoxia and exercise for 15 subjects, each receiving both treatments in sequence, were generated using the following assumptions:

- 15 simulated subjects were randomised to one of the two available treatment sequences (see Section 6.2) using block randomisation with block size of 4 records
- PASP at baseline and under hypoxia and exercise for both treatment groups (a total of four PASP measurements per subject) were sampled from a multivariate normal distribution, using values for mean PASP, standard deviation of PASP and within-subject correlation of PASP as described below.
- Mean PASP was 30 mmHg at baseline (i.e. normoxic and at rest) for both treatments, and 45 mmHg under hypoxia and exercise for Placebo (as in Section 9.2.1). For GSK2586881, mean PASP under hypoxia and exercise was $(45 - \Delta)$ mmHg, where Δ (the mean treatment difference) was varied according to four different scenarios:
 - no treatment difference ($\Delta = 0$ mmHg)
 - weak treatment difference of a magnitude of half the clinically meaningful difference ($\Delta = 2.5$ mmHg)
 - minimum clinically meaningful difference ($\Delta = 5$ mmHg)
 - overwhelming treatment difference one-and-a-half times the clinically meaningful difference ($\Delta = 7.5$ mmHg)
- SD of PASP was 2.81 mmHg at baseline and 4.30 mmHg under hypoxia and exercise, for both treatment groups (as in Section 9.2.1)

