- The within-subject correlation of PASP was unknown, therefore four different scenarios of within-subject correlation were evaluated: zero correlation, low correlation (0.3), high correlation (0.6) and very high correlation (0.9) (as in Section 9.2.1). Within-subject correlation of PASP was assumed to be compound symmetric (i.e. the same correlation was used for each of the six possible pairs of the four PASP measurements within each subject).

- It was assumed that there would be no effect of period in the simulation, i.e. it was assumed that it would make no difference if the measurement was taken from the first or second chronological period in the treatment sequence.

Modelling took on a three-step process, with decisions after each. Firstly, the treatment difference and its associated standard error was then estimated for the dataset of 15 simulated subjects using a mixed effects linear regression model, including covariates for period, treatment, period baseline and subject baseline (the mean of the two period baselines) as fixed effects and subject as a random effect. If the sign of treatment difference arising from the simulated data was in the wrong direction (i.e. the simulated outcome for GSK2586881 was worse than for Placebo), then the simulated study was stopped for futility.

Secondly, in the alternative case that the simulated treatment difference was in favour of GSK2586881 over Placebo, a posterior probability of success (where success was defined as a 97.5% posterior probability of the treatment difference being in favour of GSK2586881 over Placebo) was evaluated for 30 subjects. This was evaluated using a t-distribution, with the mean and standard deviation taken as the treatment difference and standard error (multiplied by a factor of the square root of 15 to estimate the standard deviation) from step one respectively, and α . If this posterior probability was less than 0.2, then the study was stopped for futility as being unlikely to show any benefit of GSK2586881 over Placebo.

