Thirdly, provided that the simulated study hadn't been stopped for futility in either of the first two steps, posterior probabilities of success were calculated for N ranging from 15 to 29 subjects. If any of these posterior probabilities of success were greater than or equal to 0.9, then the study was continued with a reduced sample size equal to the lowest N at which that threshold was reached. Otherwise, the conclusion from the simulated interim analysis would be to continue the study with unchanged sample size.

This whole process (simulating data for 15 subjects, modelling the treatment difference, evaluating posterior probabilities of success and simulating the decision-making process) was replicated 1000 times for each scenario, with the decision ("futile", "no change to N" or "reduce N") recorded for each iteration. Each combination of the four treatment difference scenarios and the four correlation scenarios was evaluated for a total of 16 scenarios in all.

The estimated proportions of each decision being reached under each of the 16 scenarios are presented in [Table 4](#).

Table 4 Operating characteristics of interim analysis under four scenarios of treatment effect and four scenarios of within-subject correlation

Treatment effect Scenario	Within-subject correlation of PASP	Frequency of decisions (%)		
		Futile	Continue with 30 subjects	Continue with reduced sample size
$\Delta=0$ mmHg (no treatment difference)				
0.0	87%	13%	0%	
0.3	87%	13%	1%	
0.6	85%	15%	0%	
0.9	86%	14%	0%	
$\Delta=2.5$ mmHg (weak treatment effect, less than clinically meaningful difference)				
0.0	31%	60%	9%	
0.3	24%	65%	11%	
0.6	10%	66%	25%	
0.9	0%	9%	91%	
$\Delta=5$ mmHg (good treatment effect, at threshold of clinical meaningful difference)				
0.0	2%	46%	52%	
0.3	1%	35%	64%	
0.6	0%	11%	89%	
0.9	0%	0%	100%	
$\Delta=7.5$ mmHg (very strong treatment effect)				
0.0	0%	10%	90%	
0.3	0%	2%	98%	
0.6	0%	0%	100%	
0.9	0%	0%	100%	

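### The end-of-study rule counts PASP success at a posterior probability above 0.95, but the interim projection of Section 9.3.2 counts it at 97.5%, with no explanation

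*Protocol*

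**What the plan says.** Protocol Section 9.1 states that no formal hypotheses are tested and gives a rule of thumb: the study is a success if the posterior probability of any PASP reduction at T3-T0 "is if the probability of any treatment related reduction in PASP (T3-T0) exceeds 0.95". That phrase is qualified by a second condition, a small probability that treatment lowers oxygen saturation by more than 5% absolute.

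Section 9.3.2 simulates the interim decision in three steps. A treatment difference in the wrong direction is futile. Otherwise success at the full sample size is projected, "where success was defined as a 97.5% posterior probability of the treatment difference being in favour of GSK2586881 over Placebo". "If this posterior probability was less than 0.2, then the study was stopped for futility". Failing that, smaller sample sizes are tried: "If any of these posterior probabilities of success were greater than or equal to 0.9", the study continues with the lowest such N.

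Both sections read this way in the original protocol and in Amendment 01, with the interim at 15 of 30 subjects. Amendment 02's list of specific changes (Section 12.6.2.2) rewrites the Section 9.3.2 paragraph for 10 of 20 subjects and keeps the bar: "success was defined as a 97.5% posterior probability of the treatment difference being in favour of GSK2586881 over Placebo". That list has no entry for Section 9.1.

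The status of these rules also matters. Section 5.4.1 says the study may be stopped, by decision of the core study team. Section 9.2.2 calls the re-estimation advisory. Section 9.3.2 leaves full interim details to the RAP.

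**The concern.** A futility projection should predict the event on which the trial will be judged. Here the contrast is the same (GSK2586881 minus placebo, T3-T0) but the bar is 0.95 at the end and 97.5% at the interim. A team reading a low projected probability of success would be reading the chance of clearing a higher bar than the one in Section 9.1.

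What is at stake is extra futility stopping when a real but modest effect exists. Section 9.1 counts any reduction, so a true 2.5 mmHg effect can meet it.

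**Working it through.** **Inputs.** SD of PASP 2.81 mmHg at baseline and 4.30 mmHg under hypoxia and exercise; compound-symmetric within-subject correlation ρ of 0, 0.3, 0.6 or 0.9; true effect Δ of 0, 2.5, 5 or 7.5 mmHg; blocks of 4; futility below 0.2, reduction at 0.9 or more (all Section 9.3.2). Interim and final N are 15/30 (Amendment 01) or 10/20 (Amendment 02).

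**Projection.** Let z be the interim estimate divided by its SE, positive in favour of the drug, from n subjects. The protocol takes SD = SE × √n and uses a t-distribution without stating the exact form. The form that gives back Table 4 is a two-sample t with N per group:

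- projected success = P(T > t[p, 2N−2]), with T noncentral t on 2N−2 df and noncentrality z × √(N/(2n)).
- When N = 2n, as in both designs, the noncentrality is z.

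**Reproducing Table 4 first** (10,000 simulated trials per scenario, p = 0.975; futile/continue/reduce, %):

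| Design, Δ, ρ | Protocol | Reproduced |
|---|---|---|
| 15/30, 2.5, 0 | 31/60/9 | 31/60/9 |
| 15/30, 2.5, 0.3 | 24/65/11 | 23/65/12 |
| 15/30, 2.5, 0.6 | 10/66/25 | 10/66/25 |
| 15/30, 5, 0 | 2/46/52 | 3/49/49 |
| 10/20, 2.5, 0 | 44/50/6 | 43/50/7 |
| 10/20, 2.5, 0.3 | 36/56/9 | 36/56/9 |
| 10/20, 2.5, 0.6 | 21/63/16 | 21/63/17 |

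At Δ = 0 the futile rate is 85-86%, against 85-87% in the 15/30 table. The 3-point gap at Δ = 5, ρ = 0 is within the error of the 1000 replicates stated for the 15/30 table (SE √(0.46 × 0.54/1000) = 1.6 points). With p = 0.95 the table does not come back: the null futile rate is 70-71% or 78%, depending on the projection form. So 97.5% was the bar actually used.

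**Futility cut-off on z.** Solve projected success = 0.2.

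- 15/30 (58 df): critical t 2.002 at 0.975 and 1.672 at 0.95, giving z = 1.14 and 0.81.
- 10/20 (38 df): critical t 2.024 and 1.686, giving z = 1.15 and 0.82.

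At z = 1.15, just on the 97.5% boundary, the projected chance of meeting 0.95 is about 1 − Φ(1.686 − 1.147) = 1 − Φ(0.539) = 0.295; the exact noncentral t value is 0.30. Trials with z between 0.82 and 1.15 are stopped although the same rule set to 0.95 would continue them.

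**Futile rate, 10/20** (%, ρ = 0/0.3/0.6):

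| Δ | bar 97.5% | bar 0.95 |
|---|---|---|
| 0 | 85-86 | 77-78 |
| 2.5 | 43/36/21 | 32/25/12 |
| 5 | 9/4/1 | 5/2/0 |

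**Trials stopped that would have met 0.95** (interim and final simulated jointly, 20,000 trials; % of all trials, ρ = 0/0.3/0.6). At 10/20, Δ = 2.5: 12.6/13.4/12.2 with 97.5%, against 7.3/7.5/6.4 with 0.95. The excess agrees with the band: at ρ = 0 it holds 10.9% of trials, 48.0% of which would exceed 0.95 if completed, and 0.109 × 0.480 = 5.2 points against 12.6 − 7.3 = 5.3. At Δ = 5: 7.5/3.9/0.7 against 3.8/1.7/0.3.

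**Sample-size step.** The z needed for a reduced N is 3.42 at 97.5% and 3.06 at 0.95 (10/20). At Δ = 5, ρ = 0, reduction is recommended in 30% of trials against 40%; at 15/30, in 49% against 60%. The stricter bar keeps more subjects.

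**Sensitivity to the projection form.** A paired projection, which does not reproduce Table 4 (null futile rate 78% at 97.5%), gives 33/25/13% against 25/18/8% at 10/20, Δ = 2.5: same direction, 5 to 8 points.

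**The case against.** The strongest reply is about status. The 0.95 figure is a rule of thumb in a study without formal hypotheses. The 97.5% figure stands in an account of a simulation, the decision to stop is discretionary, the re-estimation is advisory, and details go to the RAP. All of that stands and limits the severity. It does not reconcile the numbers: the protocol fixes both, so a RAP must depart from one of them, and discretion does not make the projection refer to the Section 9.1 event.

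A stricter interim bar could be deliberate, and it stops an inactive drug more often. That is possible, but no section shown says so.

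The protocol also calls 2.5 mmHg less than clinically meaningful and accepts that such a drug may be stopped. Any futility rule loses some eventual successes. Both are true. The comparison above isolates the excess due to the mismatch, and at 5 mmHg that excess is small.

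A reader might infer that 97.5% is the wrong number, or that every recommended N and all of Table 4 are invalid. The documents do not support this. They do not say which threshold was intended. Table 4 reports decision frequencies and reproduces at the stated 97.5%. In the sample-size step the stricter bar errs toward more subjects.

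**Conclusion.** The inconsistency is real: two success thresholds for one contrast, unexplained. The consequence is confined to the futility step. At 10/20 it adds about 9 to 11 points of futile stopping at 2.5 mmHg, about 8 points under no effect and about 0 to 5 points at 5 mmHg. Trials stopped that would have met 0.95 at 2.5 mmHg are about 12-13% of all trials, against 6-8% with aligned thresholds.

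These sizes rest on the protocol's SDs and correlation scenarios, on the projection form inferred from Table 4, and on the rule being followed as simulated. The saturation condition of Section 9.1 is not modelled, so they concern the PASP part of success only. Amendment 02's own Section 9.1 is not shown; that it still says 0.95 is inferred from its change list.

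It might be tempting to read this as an interim that is bound to end trials that would succeed, and so as a critical defect. The discretionary wording of Sections 5.4.1 and 9.2.2 and the exploratory aim do not bear that out. It should be fixed.

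**What to change.** Use one threshold in Sections 9.1 and 9.3.2, and settle it before the unblinded interim so that the choice cannot depend on the data. There are two options:

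- Set the Section 9.3.2 success event to a posterior probability above 0.95, state that the projection covers the PASP part of success only, re-run Table 4 and correct the accompanying text on how often an ineffective drug is stopped. Cost: one number and one simulation run. Futility stopping under no effect falls from about 85% to about 78%, which weakens the stated aim of stopping in the overwhelming majority of such cases.
- Change the Section 9.1 rule of thumb to 0.975. Table 4 then stands on this point. Cost: one number, and a stricter end-of-study bar.

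If different bars are intended, Section 9.3.2 should say so, give the reason and report the extra futility stopping.
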